11.2 Data and Safety Monitoring Plan

The Stanford Cancer Institute Data and Safety Monitoring Committee (DSMC) will be the monitoring entity for this study. The DSMC will audit study-related activities to determine whether the study has been conducted in accordance with the protocol, local standard operating procedures, FDA regulations, and Good Clinical Practice (GCP). This may include review of the following types of documents participating in the study: regulatory binders, case report forms, eligibility checklists, and source documents. In addition, the DSMC will regularly review serious adverse events and protocol deviations associated with the research to ensure the protection of human subjects. Results of the DSMC audit will be communicated to the IRB and the appropriate regulatory authorities at the time of continuing review, or in an expedited fashion, as needed.

11.3 Data Management Plan

The Protocol Director, or his/her designee, will prepare and maintain adequate and accurate participant case histories with observations and data pertinent to the study. Study specific Case Report Forms (CRFs) will document treatment outcomes for data analysis. Case report forms will be maintained by Stanford Box account, a secure data storage platform, or in a locked office accessible only to the research team.

12. STATISTICAL CONSIDERATIONS

12.1 Statistical Design

This study is a randomized double-blind, placebo-controlled clinical trial.

12.1.1 Randomization

Patients will be randomized within their group (unilateral or bilateral reconstruction) to receive either a true TAP catheter or a sham TAP catheter with saline infusion. The Stanford Pharmacy will randomize patients into the two groups.

12.2 Interim analyses

There are no planned interim analyses.

12.3 Descriptive Statistics and Exploratory Data Analysis

If applicable, describe plans for descriptive statistics and exploratory data analysis.

12.4 Primary Analysis

Post-operative Narcotic Usage

12.4.1 Analysis Population

Subjects will be grouped according to laterality of breast reconstruction (i.e., unilateral vs. bilateral). Within each group, experiment subjects will be compared to control subjects. A first

sensitivity analysis will explore the impact of missing data by replacing missing data with the more extreme values that favor the null hypothesis. A second sensitivity analysis will replace missing values with an extreme value that favors the alternative hypothesis. In both cases "extreme" is the largest or smallest value as applicable.

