1. OBJECTIVES

1.1. Primary Objective

The primary objective is to determine if pre-operative transversus abdominis plane (TAP) blocks with continued infusion of local anesthetic post-operatively affect post-operative narcotic usage as compared to a placebo TAP block.

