48 hours after surgery. However, in this study only a single injection of local anesthetic was given intra-operatively, and this injection was performed by a surgeon in the operating room, rather than by an anesthesiologist in the pre-operative waiting area. The duration of block placement varied between 18 and 24 minutes, increasing the overall length of time in the operating room. In addition, Hivelin et al. only followed patients to 48 hours after reconstruction.¹⁵ Furthermore, Wheble et al. performed a retrospective review of intra-operatively placed TAP blocks and found patients receiving the block had a shorter hospital length of stay, lower overall morphine usage, and less post-operative nausea and vomiting. However, this was a retrospective study with a small number of patients in each group (12 in the TAP group, and 15 in the non-TAP group).¹⁶

In addition, Zhong et al. conducted a prospective cohort study with TAP block catheters placed intra-operatively under direct visualization of fascial planes, and the anesthetic infusions continued until post-operative day 3. Zhong et al. compared this group of patients to a retrospective cohort from the same institution and found that patient who received TAP blocks had significantly less opioid usage than those who did not.¹⁷ The group conducted a subsequent randomized double-blinded controlled trial with TAP catheters placed under direct vision, this time administering either local anesthetic or saline for controls and found similar results.¹⁸

A limitation of both studies by Zhong et al. is that patients undergoing both unilateral and bilateral reconstruction were combined, as were patients undergoing immediate and delayed reconstruction. Given that patients are subjected to twice the surgical insult in bilateral versus unilateral reconstruction, combining these patients into one cohort for analysis of post-operative pain may confound the results attained. Similarly, in delayed reconstruction, a repeat surgical incision is made at the site of the breast, whereas in immediate reconstruction, the same incision at the breast is used for both mastectomy and reconstruction.

In our study design, patients undergoing unilateral and bilateral reconstruction will be separated for both randomization and statistical analysis. We aim to further elucidate if the specific type of surgery changes the efficacy of the pre-operative TAP nerve block.

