3.4 Randomization Procedures

Patients will be randomized within their surgery subtype (unilateral or bilateral) by the Stanford

Pharmacy to receive TAP catheters infusing either bupivacaine or saline. Randomization will occur using a computer software program to be implemented by the Pharmacy. The anesthetist placing the block, the surgeon performing the surgery, the nurses caring for the patient while hospitalized, and the research coordinators collecting data will be blinded to the randomization status.

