12.4.2. Analysis Plan

Differences between the two arms will be evaluated using an analysis of covariance model. The comparison of the two arms will be made adjusting for the variables used in the stratified randomization. The primary analysis will be a modified intent-to-treat principle (using recorded values where available regardless of compliance).

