12.5.2 Post-operative Anti-emetic Usage

12.5.2.1 Analysis Population

Subjects will be grouped by study intervention, with experimental subjects being compared to control subjects. Missing data will be dropped, and subjects who were non-adherent to the protocol will be excluded.

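### The primary narcotic-use comparison is described both as separate tests within each laterality group and as one pooled two-arm test; nothing says which is primary, and the 80% power belongs to the pooled test only

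*Combined protocol and SAP*

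**What the plan says.** Two places separate the laterality groups. Section 2.3, after criticising earlier studies for mixing unilateral and bilateral cases, says that "patients undergoing unilateral and bilateral reconstruction will be separated for both randomization and statistical analysis". Section 12.4.1, for the primary outcome, groups subjects by laterality and continues: "Within each group, experiment subjects will be compared to control subjects".

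The remaining places describe a single comparison.

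- Section 1.1 asks whether the active block will "affect post-operative narcotic usage as compared to a placebo TAP block", with no split by laterality.
- Section 12.4.2 specifies an analysis of covariance: "The comparison of the two arms will be made adjusting for the variables used in the stratified randomization". Laterality is the only stratifier named, in 3.4 and 12.1.1.
- Section 12.6.1 sets the target at 64 per arm, 128 in all.
- Section 12.6.2 has one null hypothesis, a 10 mg difference, an SD of 20 mg, a two-tailed t-test and 80% power. It gives no alpha and does not say whether 20 mg is the overall SD or the SD within a laterality group.

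Section 2.3 also sets a further aim: "We aim to further elucidate if the specific type of surgery changes the efficacy of the pre-operative TAP nerve block". Section 12 plans no estimate or test of a treatment-by-laterality interaction.

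**The concern.** A statistician following 2.3 and 12.4.1 would run two tests. One following 12.4.2 would run one. If laterality is the only stratifier, the adjustment in 12.4.2 has nothing to act on inside a single laterality group, so the two sections cannot both be applied literally.

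The within-group wording is hard to dismiss as loose drafting, because the plan uses different words where it means to pool. For anti-emetic use, 12.5.2.1 says "Subjects will be grouped by study intervention, with experimental subjects being compared to control subjects", and the two time-to-event outcomes and quality of life use the same form. Only narcotic use and pain score are grouped by laterality.

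At stake is whether the confirmatory test is fixed in advance. If it is not, the reading could be settled after the data are seen. The stated power may also not apply to the test that is run. And a result that is significant in one laterality group only could be taken as evidence that efficacy depends on the type of surgery.

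**Working it through.** **Inputs.** From 12.6.2: difference 10 mg, SD 20 mg, two-tailed t-test, 80% power. From 12.6.1: 64 per arm, 128 in total. Assumed: two-sided alpha 0.05; equal allocation within each laterality group; no dropout; the unilateral/bilateral split, shown as a range because the documents give none.

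**Formula.** With n per arm, λ = 10 / (SD × √(2/n)), and power = P(|T| > t(0.975, 2n − 2)), where T is noncentral t with 2n − 2 degrees of freedom and noncentrality λ.

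**Step 1: the plan's own figure.** For n = 64, λ = 10 / (20 × √(2/64)) = 2.83 and power is 80.1%; 63 per arm gives 79.5%. So 64 per arm reproduces. The alpha assumption is supported by this: 0.10 would need 51 per arm and 0.025 would need 78. The pooled ANCOVA with a laterality term (125 residual degrees of freedom, no variance reduction) also has 80.1%.

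**Step 2: separate tests, taking 20 mg as the within-group SD.** *Both* is the product p₁p₂ and *exactly one* is p₁(1 − p₂) + p₂(1 − p₁).

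| Split | n per arm, larger / smaller group | λ | Power | Both significant | Exactly one |
|---|---|---|---|---|---|
| 50/50 | 32 / 32 | 2.00 / 2.00 | 50% / 50% | 25% | 50% |
| 60/40 | 38 / 26 | 2.18 / 1.80 | 58% / 42% | 24% | 51% |
| 70/30 | 45 / 19 | 2.37 / 1.54 | 65% / 32% | 21% | 55% |
| 80/20 | 51 / 13 | 2.52 / 1.27 | 71% / 23% | 16% | 61% |

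**Step 3: if 20 mg is the overall SD.** The within-group SD is then √(400 − p(1 − p)D²), where p is the smaller group's share and D is the difference in mean use between laterality groups. The documents do not give D, so these are illustrations.

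- D = 20 mg, even split: SD = √(400 − 0.25 × 400) = 17.3 mg, power 62% in each group.
- D = 30 mg, even split: SD = √(400 − 0.25 × 900) = 13.2 mg, power 85% in each group.
- D = 30 mg, 70/30: SD 14.6 mg, power 90% and 54%.
- D = 30 mg, 80/20: SD 15.9 mg, power 88% and 34%.

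**Step 4: how often the two readings reach different conclusions.** This was simulated with 40,000 trials per split, a true 10 mg effect in both groups and a within-group SD of 20 mg. The pooled ANCOVA at 0.05 was compared with each possible rule for combining two separate tests. Ranges cover even to 80/20 splits.

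| Rule for the separate tests | Different conclusion |
|---|---|
| At least one group significant, each at 0.05 | 10% to 13% |
| At least one group significant, each at 0.025 | 17% to 22% |
| Both groups significant, each at 0.05 | 55% to 64% |

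The last row can be checked by hand, since two significant groups almost always make the pooled test significant: 80.1% − 25.4% ≈ 55% at an even split and 80.1% − 16.3% ≈ 64% at 80/20. The first rule also has a cost under the null: its familywise error is 1 − 0.95² = 9.75%.

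**Step 5: power for the aim in 2.3.** The interaction has SE = 20 × √(2/n₁ + 2/n₂), which is 7.07 mg at 32/32 and 8.79 mg at 51/13. For an assumed 10 mg difference in effect between laterality groups, power is 29% and 20%.

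**The case against.** The strongest reply is that the text can be reconciled. Section 12.4.1 is headed as the analysis population, and the test itself is set out in 12.4.2. In an additive ANCOVA with laterality as a covariate, the treatment estimate is a weighted average of the within-laterality differences, so comparing arms within each group may simply describe what that model does. That the adjustment is idle inside one laterality group then counts in favour of the pooled reading. The objective, the total of 128 and the single null hypothesis point the same way.

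Most of this stands. The pooled reading is the more likely intention. But it is written nowhere, 2.3 says the groups are separated for analysis, and the plan uses different wording where it means to pool.

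Two stronger readings are tempting and do not hold. A reader might infer that the sample size is wrong; it is not, because it reproduces for the pooled test. A reader might also infer that the two approaches usually disagree, from the 55% to 64% figure. That figure requires both laterality groups to be significant, which the plan does not say. If one significant group suffices at 0.05, disagreement falls to 10% to 13%.

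It is also fair to object that the split and D have no source in the documents. The loss of power under separate tests is therefore conditional. Nor do the documents show any intention to choose the reading after the fact; they only leave room for it.

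**Conclusion.** The primary test is not uniquely defined, and that needs correcting. The size of the consequence depends on inputs the plan does not give.

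- Pooled reading: the stated 80% stands, at an assumed two-sided alpha of 0.05.
- Separate tests with 20 mg as the within-group SD: each group falls short of 80% at every split examined, most severely the smaller group when the split is uneven.
- Separate tests with 20 mg as the overall SD: power is higher and can pass 80% in both groups, but among the cases shown only at an even split with laterality means 30 mg apart.
- Divergent conclusions: from about one trial in ten to nearly two in three, according to a combination rule that is absent.
- With a uniform 10 mg effect and a within-group SD of 20 mg, about 50% to 61% of trials would show significance in exactly one group. That pattern would not by itself be evidence that laterality modifies the effect.

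**What to change.** In 2.3, 12.4.1 and 12.4.2, name one primary test: the ANCOVA of 48-hour oral morphine equivalents on treatment and laterality, in all randomised patients with recorded values. List the stratification variables by name. Report the within-laterality effects with confidence intervals, and the treatment-by-laterality interaction, as secondary; say that the interaction addresses the aim in 2.3 and has low power. In 12.6.2, state the alpha, say which SD the 20 mg is, and state that the 80% power applies to the pooled comparison and is not claimed within laterality groups.

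This is a change of wording and needs no extra patients. Its downside is that by-laterality results become secondary, although 2.3 criticises earlier studies for combining the groups. The laterality term and the secondary estimates answer that only in part.

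If separate primary tests are really intended, 12.6 must size each laterality group and give a combination and multiplicity rule. With a within-group SD of 20 mg that means at least 4 × 64 = 256 patients with each test at 0.05, or 4 × 78 = 312 with each at 0.025, and more if the split is uneven. At the estimated 40 eligible patients a year in 12.6.1, 256 would take 256/40 = 6.4 years even if all enrolled, against about 48 months to primary completion in 3.5. Both accrual figures are estimates, and 12.6.1 allows enrolment to continue until the target is met.

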12.4.2. Analysis Plan

Differences between the two arms will be evaluated using an analysis of covariance model. The comparison of the two arms will be made adjusting for the variables used in the stratified randomization. The primary analysis will be a modified intent-to-treat principle (using recorded values where available regardless of compliance).

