9. STUDY CALENDAR

	Pre-Study	POD 0	POD 1	POD 2	POD 3-Discharge	1-6 months post-operatively
Investigational Treatment		X	X	X		
Informed consent	X					
Demographics	X					
Medical history	X					
Height	X					
Weight	X					
TAP catheter		X	X	X		
PCA		X	X	X		
Adverse event evaluation		X	X	X	X	
Evaluation for discharge ^a		X	X	X	X	
Pain evaluation	X	X	X	X	X	
BREAST-Q questionnaire	X					X

^aPatients will be evaluated daily for meeting discharge criteria and discharged when all criteria are met (detailed in Section 4.2.5).

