10.1 Primary Outcome Measure: Post-operative Narcotic Usage

10.1.1 Measurement Definition

Post-operative Narcotic Usage will be measured in total oral morphine equivalents (OME) calculated by summing all narcotics used in the first 48 hours post-operatively.

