12.6.2 Sample size justification

The target sample size was determined by the two-tailed t-test power calculation. The estimated standard deviation of total oral morphine or equivalents is 20 mg. A difference of 10 mg between the two arms is considered clinically relevant. To detect a difference of 10mg of morphine (or oral morphine equivalents) between the experimental and control groups with a power of 80%, we calculated a target enrollment of 64 patients in each group. The null hypothesis is that the experiment and control groups will not have significantly different Post-operative Narcotic Usages in the first 48-hour period post-operatively. The alternative hypothesis is that the experiment and control groups will have significantly different Post-operative Narcotic Usages in the first 48-hour period post-operatively

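### The primary ANCOVA is valid but adjusts for laterality alone; pre-specifying age and weight, and pre-study pain once it is defined, costs almost nothing and may add power

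*Combined protocol and SAP*

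**What the plan says.** - **Primary outcome.** Section 10.1.1 defines narcotic use in oral morphine equivalents (OME), "calculated by summing all narcotics used in the first 48 hours post-operatively".
- **Primary model.** Section 12.4.2 specifies an ANCOVA and gives its covariates in one sentence: "The comparison of the two arms will be made adjusting for the variables used in the stratified randomization". Sections 3.4 and 12.1.1 show that randomisation is stratified by laterality only (unilateral or bilateral). No other covariate is named for this outcome.
- **Baseline data.** The Section 9 calendar marks demographics, height, weight and "Pain evaluation" in the Pre-Study column. Age is not a line of its own; it follows from demographics and from the age criterion in Section 3.1.
- **Pre-operative visit.** Section 4.1 covers screening, enrolment, consent and the BREAST-Q, with no pain score. Section 10.2 defines the VAS as a post-operative measure and gives only post-operative time points.
- **Sample size.** Section 12.6.2 rests on a two-sided t-test. On variability it says: "The estimated standard deviation of total oral morphine or equivalents is 20 mg". It takes 10 mg as the gap that matters clinically and reports, "with a power of 80%, we calculated a target enrollment of 64 patients in each group". It states no alpha and does not say whether the SD is overall or within laterality.

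**The concern.** Weight, age and pre-study pain are fixed before any study infusion, so treatment cannot affect them, and each might help to predict how much opioid a patient takes. Any outcome variance that they explain stays in the error term if they are left out. Since the plan already uses ANCOVA, adding them means naming covariates in a model that exists, not changing the method.

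Two things are at stake: precision on the primary comparison, and protection against chance imbalance in these variables among 128 patients. Both require the covariates to be fixed in advance, because covariates chosen after unblinding would be open to challenge.

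**Working it through.** **Inputs from the documents (Sections 12.6.1 and 12.6.2):** difference 10 mg OME, SD 20 mg, 64 per arm, power 80%, two-tailed t-test.

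**Assumptions:** two-sided alpha 0.05; 20 mg is the SD remaining after laterality; R² is the share of that remaining variance explained by the added covariates. The documents give no value for R², so a range is shown.

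**Step 1: reproduce the plan's figure.** Noncentrality = difference / (SD × √(2/n)) = 10 / (20 × √(2/64)) = 2.828, on 126 degrees of freedom. The two-sided noncentral-t power is 80.1% at 64 per arm and 79.5% at 63, so 64 is the smallest sufficient number. The plan's figure reproduces, which supports the assumed alpha. A one-sided test would need about 50 per arm, which does not match.

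**Step 2: cost of the extra covariates.** With laterality only, df = 128 − 2 − 1 = 125 and power is 80.14%. With laterality, age, weight and pain, df = 128 − 2 − 4 = 122 and power at R² = 0 is 80.13%. The cost is about 0.01 percentage points, and it is recovered at an R² of roughly 0.0005.

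**Step 3: possible gain.** Residual SD = 20 × √(1 − R²); noncentrality = 2.828 / √(1 − R²); df = 122. The last column is 64 / (1 − R²), the unadjusted number per arm that would give about the same precision.

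| R² | Residual SD (mg) | Noncentrality | Power at 64 per arm | Equivalent n per arm |
|---|---|---|---|---|
| 0 | 20.00 | 2.828 | 80.1% | 64 |
| 0.02 | 19.80 | 2.857 | 80.9% | 65 |
| 0.05 | 19.49 | 2.902 | 82.1% | 67 |
| 0.10 | 18.97 | 2.981 | 84.1% | 71 |
| 0.20 | 17.89 | 3.162 | 88.0% | 80 |

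With age and weight alone, df is 123 and the powers are the same to one decimal place, or differ by 0.1 point at most, for a given R². The R² itself may of course be smaller without pain.

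**Step 4: where these figures apply.** They describe the single laterality-adjusted comparison in Section 12.4.2. Section 12.4.1 also speaks of comparing arms within each laterality group. If those separate comparisons were the primary tests, an assumed even split of 32 per arm per stratum gives noncentrality 10 / (20 × √(2/32)) = 2.0 and power of about 50%. The table would not apply.

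**The case against.** The strongest reply is that nothing here is wrong. An ANCOVA adjusted for the stratification variable is valid, matches the randomisation and raises no bias or type I error problem. This stands: the point is an improvement, not the correction of an error.

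Three stronger readings are tempting, and the documents support none of them.

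- **That the plan gives up a known amount of power.** The gain depends wholly on an R² that appears nowhere. Pre-study pain in particular may vary little, since Section 3.2 excludes patients with recent chronic pain on opioids and Section 3.1 admits prophylactic patients.
- **That the primary analysis has no power to spare.** The 80.1% belongs to the unadjusted t-test in Section 12.6.2 at an assumed alpha, whereas the planned test already adjusts for laterality. Section 2.3 describes bilateral surgery as a double surgical insult, so laterality may explain some of the variance. If 20 mg is the overall SD, the planned adjustment may already bring power that the calculation does not claim; if it is the within-laterality SD, it brings none. The text does not settle which.
- **That all three covariates are in hand for every patient.** Only weight is named and uncontested. Age is inferred. Pre-study pain rests on one calendar mark, with no instrument or timing defined for it.

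A last objection is that the tension between Sections 12.4.1 and 12.4.2 is the larger power question. On the figures above that is fair, but it is a separate matter and does not remove this one.

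**Conclusion.** The point holds as a low-cost improvement to a valid analysis. Section 12.4.2 limits the primary model to laterality although weight and age, and according to the calendar a pain evaluation, are scheduled before surgery.

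The benefit ranges from practically nothing at R² near zero to about 2 percentage points of power at 0.05, 4 at 0.10 and 8 at 0.20; which of these applies cannot be known from the documents. The cost in degrees of freedom is negligible across the range. The figures rest on a two-sided alpha of 0.05, a 20 mg SD after laterality, complete outcome data on 64 per arm, and one adjusted comparison as the primary test.

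**What to change.** Before unblinding:

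1. In Section 12.4.2, specify the primary ANCOVA as arm, laterality, age and body weight, with the last two continuous and linear.
2. Reconcile the Pre-Study pain entry in Section 9 with Sections 4.1 and 10.2. If a pre-operative score is collected, list it in Section 4.1, state its instrument and timing in Section 10.2, and add it to the model as a continuous linear term. If it is not, correct the calendar and keep the model in item 1.
3. State that a missing baseline covariate is filled with the overall mean across both arms, so that no patient leaves the primary analysis for that reason.

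The cost is a sentence or two in Section 12.4.2, a line in Section 4.1 and a short definition in Section 10.2. It needs no extra patients. Age and weight need no new data collection; pain needs none only if the calendar entry is already being followed.
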